### **2.2 Secondary Objectives**

To determine if treatment with belatacept better preserves GFR in those patients with marginal renal function as compared to those patients who continue calcineurin inhibitor therapy and as a result delays time to initiation of dialysis. Subjects already requiring dialysis at the time of enrollment will be excluded from this analysis.

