**Secondary Endpoints:**

-Rate of change in GFR compared to participants maintained on CNI-based or mTOR-based regimen. Subjects already requiring dialysis will be excluded from this endpoint analysis.

-Time to dialysis measured from the time of randomization to initiation of dialysis compared to participants maintained on CNI-based or mTOR-based regimen.

Subjects already requiring dialysis at the time of enrollment will be excluded from this endpoint analysis.

- Overall level of alloantibody as indicated by PRA.
- Incidence of infectious complications.

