#### **2) Target Population**

- a) The subject is a kidney transplant recipient (non-HLA identical donor) who now has impaired renal allograft function with at least one of the following:
  - i) Estimated GFR  $\leq 35$  with a decline in GFR of  $\geq 10\%$  in the 12 months prior to enrollment and must have biopsy proven grade II or III interstitial fibrosis/tubular atrophy (IF/TA)
  - ii) Estimated GFR persistently  $\leq 20$  ml/min over the 6 month period prior to enrollment absent other causes for graft dysfunction, and deemed to have a failing allograft by the patient's transplant nephrologist
- b)  $\geq 1$  year post-transplant
- c) The subject must be a re-transplant candidate
- d) The subject must be on an immunosuppression regimen meeting one of the following criteria:
  - i) A CNI (tacrolimus or cyclosporine) or mTOR inhibitor (sirolimus or everolimus) and at least one of the following:
    - (1) MMF at a dose of at least 1 gm/day or comparable dose of MPA or azathioprine
    - (2) Prednisone at a dose of at least 5 mg/day
  - ii) A CNI (tacrolimus or cyclosporine) or mTOR inhibitor (sirolimus or everolimus) alone for 3 months or more, with no clinically significant changes in PRA during that time, as determined by the Emory HLA lab.

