### **6.6.2 Secondary Efficacy Assessments**

Secondary endpoints will include assessment of renal function including estimated GFR and rate of change in GFR, the need for and time to initiation of dialysis, the overall level of alloantibody as indicated by PRA and the incidence of infectious complications. GFR will be calculated based upon serum creatinine using the Diet in Renal Disease (study) formula as suggested by Levey et al. Subjects already requiring initiation of dialysis at

the time of enrollment will be excluded from the need for and time to initiation of dialysis analysis.

$$\text{GFR} = 170 \times (\text{SCr}/0.95)^{(-0.999)} \times (\text{Age})^{(-0.176)} \times (0.762 \text{ if the patient is female}) \times (1.180 \text{ if the patient is black}) \times (\text{BUN})^{(-0.170)} \times (\text{Alb})^{(0.318)}$$

GFR-glomerular filtration rate (ml/min), SCr-serum creatinine (mg/dL), Age in years, BUN- blood urea nitrogen (mg/dL), Alb-serum albumin (g/dL)

Laboratory efficacy parameters will be evaluated utilizing the main laboratory results

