Analysis of secondary endpoints will be performed at the end of the study period. Differences in the mean level of allo-antibody (ie PRA) by control and belatacept-treated groups will be compared using a t-test statistic. The rate of decline of GFR among the belatacept group will be compared to the rate of decline of the control group using a Rate Ratio and corresponding 95% Confidence Intervals using the Mantel-Haenszel chi-square test statistic for significance. The time from randomization to initiation of dialysis will be compared between groups using Kaplan-Meier analysis and the log-rank test for significance. The small subset of subjects already requiring dialysis at the time of enrollment will be excluded from this analysis. The incidence of overall infectious episodes will be compared among the belatacept vs. control group by calculating a Risk Ratio and corresponding 95% Confidence Intervals and using the Mantel-Haenszel chi-

square test statistic for significance. For all secondary endpoint analyses, two-tailed  $p < 0.05$  will be considered statistically significant.

Interim analyses will be performed at 18 months to compare the primary endpoint between the belatacept-treated and control groups, using the log-rank test for significance. A two-sided test with a more stringent significance level of 0.001 will be used to preserve the overall significance level of the trial.

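### Section 8.3.3 tests GFR decline, a continuous slope, with an event-rate ratio and a Mantel-Haenszel chi-square, although no GFR event or person-time is defined

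*Combined protocol and SAP*

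**What the plan says.** **Endpoint.** Section 2.2 lists "Rate of change in GFR compared to participants maintained on CNI-based or mTOR-based regimen" as a secondary endpoint, and section 8.2 repeats it in shorter form. Section 6.6.2 describes "assessment of renal function including estimated GFR and rate of change in GFR". On measurement it says: "GFR will be calculated based upon serum creatinine using the Diet in Renal Disease (study) formula". The result is a continuous value in ml/min.

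**Analysis.** Section 8.3.3 compares the belatacept arm's rate of GFR decline with the "rate of decline of the control group using a Rate Ratio and corresponding 95% Confidence Intervals using the Mantel-Haenszel chi-square test statistic". Secondary endpoints are tested two-sided at 0.05. The synopsis says only that GFR and its change will be evaluated by standard methods.

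**The other secondary endpoints in the same paragraph.** For PRA, also continuous, the rule is: "Differences in the mean level of allo-antibody (ie PRA) by control and belatacept-treated groups will be compared using a t-test statistic". Time to dialysis gets Kaplan-Meier and log-rank. Infections get a risk ratio with a Mantel-Haenszel test.

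**Who and which values count.** Section 2.2 says of the secondary objective: "Subjects already requiring dialysis at the time of enrollment will be excluded from this analysis". It says of the GFR endpoint: "Subjects already requiring dialysis will be excluded from this endpoint analysis". Section 8.3.3 states this exclusion only after the time-to-dialysis sentence. No section says what happens to eGFR values obtained after a subject starts dialysis, or is re-transplanted, during the study.

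**The concern.** A rate ratio in the Mantel-Haenszel sense divides one event rate by another. In the GFR sentence, rate means a slope in ml/min per unit time. The two uses share a word but not a data structure: a slope supplies no event count for the numerator and no person-time for the denominator.

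Preservation of GFR is part of the research hypothesis and of the secondary objective, and section 8.3.3 attaches a significance threshold to it. To run the analysis, someone must decide what counts as a GFR event, or replace the method. The trial is open-label, so nothing in the plan prevents that decision from being made after the data have been seen by arm.

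The rule for late values is a second, smaller gap. Creatinine-based values on dialysis do not describe the allograft's decline in the same way as earlier values. Values from a new graft would count as preserved function of the old one.

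**Working it through.** **1. Is there an event anywhere?** The plan states no sample size, power, SD or effect for GFR, so there is no figure to reproduce. The check is of the text.

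| Place | What it gives | Event or person-time? |
|---|---|---|
| Synopsis, Statistics | GFR and change in GFR, standard methods | No |
| 2.2 and 8.2 | Rate of change in GFR | No |
| 4.2.1, item 2(a)(i) | Fall of at least 10% in the year before enrollment | Threshold for entry, not an outcome |
| 6.6.2 | eGFR formula, ml/min | No |
| 8.3.3 | Rate ratio, Mantel-Haenszel | Method only |

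Dialysis, the obvious renal event, cannot be the implied one because it has its own log-rank analysis.

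**2. Does the choice of event matter?** Every eGFR parameter here is assumed:
- baseline mean 25, SD 5 (range 12 to 35)
- mean slopes -3.5 (control) and -1.5 (belatacept) mL/min/year
- between-patient slope SD 2 to 5, residual SD 2
- the 11 pre-dialysis laboratory visits of Table 6.1 (months 0, 1, 2, 3, 6, 9, 12, 18, 24, 30, 36)
- dialysis at a true eGFR of 10
- 1,500 simulated trials per setting (Monte Carlo error of a percentage up to 1.3 points)

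The event is the first measured fall of the stated size, or dialysis. Median rate ratio at 36 per arm:

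| Slope SD | 20% fall | 30% | 40% | 50% |
|---|---|---|---|---|
| 2 | 0.49 | 0.42 | 0.36 | 0.31 |
| 5 | 0.66 | 0.65 | 0.64 | 0.63 |

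The same true difference gives visibly different answers when patients' slopes are similar, and nearly the same answer when they vary widely.

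**3. Could a ratio of mean slopes be meant?** It can be computed, but Mantel-Haenszel supplies neither its test nor its interval. The usual interval is Fieller's, which is unbounded when t² × var(control mean slope) ≥ (control mean slope)². At 36 per arm and slope SD 5, ignoring measurement error, the standard error is 5/√36 = 0.83. A control slope of -3.5 is then 3.5/0.83 = 4.2 standard errors from zero, while -1.5 is only 1.5/0.83 = 1.8. Simulated share of trials with an unbounded 95% interval, at slope SD 2/3/4/5:

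| Slopes (control, belatacept) | 36 per arm | 18 per arm |
|---|---|---|
| -3.5, -1.5 | 0.0/0.0/0.1/1.4% | 0.0/0.4/7.5/20.3% |
| -1.5, -0.5 | 2.0/19.2/45.0/59.7% | 18.5/45.3/67.7/77.3% |

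The second row uses 600 trials per setting (error up to 2.0 points). Eighteen per arm is shown because Phase II is contingent on funding and Phase I results. A difference in slopes does not have this problem.

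**4. What could one re-transplanted subject do?** Take a noise-free subject with baseline 25 and slope -3.5, with values after re-transplantation at month 12, 18 or 24 set to 40, 50 or 60. Fit a least-squares line over the 11 visits. With t in years, the mean of t is 1.068 and the sum of squares about it is 10.86.
- Smallest slope (month 24, eGFR 40): 45.26/10.86 = +4.17
- Largest slope (month 12, eGFR 60): 169.05/10.86 = +15.57

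The shift in the arm mean is (fitted slope + 3.5)/n:
- n = 36: 7.67/36 = 0.21 to 19.07/36 = 0.53 mL/min/year
- n = 18: 7.67/18 = 0.43 to 19.07/18 = 1.06

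The assumed treatment difference is 2.

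**5. Would a slope comparison lose power?** Not under these assumptions. At slope SD 2/3/4/5, a Welch test on per-patient slopes has power 97/76/52/36% at 36 per arm, against 80/52/34/26% for a rate ratio on a 30% fall. At 18 per arm the figures are 77/48/29/21% against 46/28/20/17%.

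**The case against.** The strongest points on the other side, and what remains of each:

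- **The synopsis allows standard methods for change in GFR, so a route to a sensible analysis exists.** True, and it confines the defect to one sentence in 8.3.3. It does not repair that sentence, which is the only specific rule for this endpoint.
- **A ratio of slopes is not named in the plan, and at 36 per arm with slopes -3.5 and -1.5 it is almost always well behaved.** Correct. The large percentages need a control slope near -1.5, about 1.5/25 = 6% a year, while the first entry route requires a fall of at least 10% in the prior year. The second entry route, by persistently low eGFR, has no such requirement, so a shallow slope is possible but not shown. This reading would not rescue the Mantel-Haenszel test in either case.
- **No visit is scheduled after re-transplantation.** Correct: Table 6.1 has pre- and post-dialysis schedules only. But section 4.2.3 does not list re-transplantation as a reason for withdrawal, and sections 4.1 and 5.4 foresee it during the trial. The re-transplant concern is therefore conditional on sampling continuing. The post-dialysis concern is not, because laboratory tests are scheduled after dialysis in both arms.
- **The power comparison assumes straight-line decline, which favours slopes.** This stands. Stopping the CNI or mTOR inhibitor in one arm only could cause an early step in eGFR, which a single slope from month 0 would mix with the trend. The power figures show only that the replacement is feasible.
- **This is one of four secondary endpoints, in a trial described as preliminary.** This also stands, and it limits the importance of the point.

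**Conclusion.** The concern holds. The method named in 8.3.3 does not match the endpoint defined in 2.2, 6.6.2 and 8.2, and nothing elsewhere supplies the event or person-time that would make it match. This conclusion rests on the text and needs no assumption about eGFR.

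The practical size is uncertain because the documents give no eGFR parameters. Under the assumed values, the choice of event ranges from important (median rate ratio 0.49 to 0.31 at slope SD 2) to negligible (0.66 to 0.63 at SD 5). One re-transplanted subject whose later values are kept could shift an arm mean by 0.21 to 0.53 mL/min/year at 36 per arm.

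The missing rule for post-dialysis and post-re-transplant values is a lesser, related gap. Only the GFR endpoint is affected. It should be corrected before any GFR analysis.

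**What to change.** In section 8.3.3:

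1. Replace the rate ratio with the between-arm difference in mean eGFR slope (mL/min per year), with a 95% CI and a two-sided 0.05 test. Use either a linear mixed model with an arm-by-time term or per-patient slopes, and name which. State how an early step in eGFR would be handled.
2. Carry over from section 2.2 the exclusion of subjects on dialysis at enrollment.
3. State that only eGFR values before on-study dialysis or re-transplantation, whichever is first, enter the slope.
4. Add one simple sensitivity analysis for truncation by dialysis, for example a fixed low eGFR value assigned at the start of dialysis.

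If the team prefers a rate ratio, defining the GFR event and its person-time before any analysis would also cure the mismatch. The slope analysis is the better fit to the stated endpoint, not the only acceptable answer.

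The cost is a wording change and a little analysis work. No visits are added, because pre-dialysis laboratory tests already fall at the same 11 time points in both arms. The schedule does not itemise BUN and albumin, which the section 6.6.2 formula needs, so confirm that they are in the laboratory panel.

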| Statistics: | 
There will be two main methods of analyzing the primary outcome at the end of the study. One will be a chi-squared test comparing the proportion of patients who developed donor-specific antibody in each study group. The second analysis will be a log-rank test comparing the survival curves (survival being defined as the time until development of donor specific antibody) between the two study groups. A separate set of similar analyses will evaluate both the need and time to initiating dialysis. Subjects requiring dialysis at the time of enrollment will be excluded from this analysis. In both calculations there are similar assumptions made; we will use a two-sided test with a significance level of 0.05 and the sample size for each arm will be 30 patients. Other measures that will be evaluated with standard statistical methods include the change in PRA, the level of allo-antibody intensity, GFR and change in GFR.
 |
|--------------------|---|

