### **5.3 Method of Assigning Subjects to a Treatment**

Subjects will be randomized in equal numbers to the following treatment groups:

- 1) CNI (tacrolimus or cyclosporine) or mTOR inhibitor (sirolimus or everolimus) based regimen (with or without MMF/MPA/azathioprine and/or steroids)
- 2) Belatacept based regimen (with or without MMF/MPA/azathioprine and/or steroids)

At the time of enrollment, immediately after written informed consent is obtained and before performing any study-related procedures, each subject will be assigned a unique sequential subject number for identification throughout the study. This subject number will not be reused for any other participant during the study. Once the subject has met all the entry criteria (inclusion and exclusion), the subject will be randomized to one of the two described treatment regimens. Adverse event reporting for all subjects will begin at the time of randomization.

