## 6.2 Screening Evaluation

Obtain written consent and enroll the subject. Consent will be obtained prior to any change in medical therapy or any procedure performed solely for the purpose of this study.

Review inclusion and exclusion criteria with patient; determine if they remain a candidate for the trial

Obtain a serum or urine pregnancy test

EBV serology done at any previous time point will be accepted for eligibility criteria and will be documented. If serology results are not available then serum will be sent for EBV antibody quantification. Both EBV and CMV viral titers will be checked prior to randomization. If the EBV viral load is positive in an EBV seropositive individual, the subject will have the EBV viral load repeated and the subject may be considered for enrollment when the result is undetectable. If CMV titer is positive, the subject will be appropriately treated and reconsidered for enrollment once the viral load is undetectable for >1 month period.

Obtain blood sample for donor specific antibody evaluation and overall allo-antibody levels. Donor specific antibody/anti-HLA antibody will be evaluated using the FlowPRA assay in the Emory University Hospital Clinical HLA Laboratory. The Emory Medical laboratory is a CLIA certified facility. If allo-antibody is detected then antigen specificity will be assessed using single-antigen HLA beads. Results from donor HLA typing will be used to determine if new anti-HLA antibody is donor specific constituting a new DSA.

Obtain a complete medical history and physical examination including a neurologic exam.

Obtain body weight (clothes on, shoes off) and height, measure vital signs (BP, HR, temp, respiration)

All women 50 years or older must have a screening mammogram, or provide results of a screening mammogram performed within the last year. Women of any age who have first degree relatives with a history of breast carcinoma or who have other risk factors of breast carcinoma must undergo increased surveillance for breast cancer according to local practice

Check and record all medications

Obtain baseline laboratory tests including serum Cr and related estimated GFR

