# **8 STATISTICAL CONSIDERATIONS**

## **8.1 Sample Size Determination**

This is a single-center, randomized, controlled trial to evaluate the efficacy of belatacept to prevent the formation of donor-specific antibody in patients with a failing renal allograft thereby preventing sensitization and facilitating re-transplantation. Based on clinical and statistical judgment, it is anticipated that a sample size of 36 patients per group will provide valuable preliminary data to assess the impact of belatacept on this growing population of patients.

The sample size for each arm will be 36 patients (Phase I 18 patients in each arm, Phase II 18 patients in each arm, total for each phase 36 patients). From previous work it is assumed that the control arm will have about 60% of patients developing antibodies within a 3 year period. (unpublished results, analysis of patients at Emory Hospital) It is proposed that the group treated with belatacept will have a dramatic decrease in allo-antibody production. Assuming a rate of 20% in the treatment group, the power would be calculated at 90%.

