### 8.3.3 Efficacy Analyses

There will be two main methods of analyzing the primary outcome at the study end. One will be a chi-squared test comparing the proportion of patients who developed donor specific antibodies in each study group. The second analysis will be a log-rank test comparing the Kaplan-Meier time to event curves between the two study groups. In both cases we will use a two-sided test with a significance level of 0.05.

The sample size for each arm will be 36 patients. This sample size calculation is based on several assumptions. We assume that the incidence of developing donor-specific antibody among the control group is 60% and among the belatacept-treated group it is 20% or less. We also assume an alpha level of 0.05 and corresponding  $Z\text{-alpha} = 1.96$  and a one-to-one ration of exposed to unexposed subjects. Calculations with these estimates yield a power of 90% to detect a three-fold difference in risk of developing donor specific antibodies between the control and belatacept-treated group.

In addition to the aforementioned assumptions, additional assumptions required for the log-rank test include no loss to follow-up in 36 months and that the distribution of the incidence of the primary endpoint follows an exponential distribution. Assuming an incidence of development of anti-donor antibody in the control group is 60% at 36 months then the hazard rate can be calculated as 0.02545. In the treatment arm, if the incidence of the primary endpoint is 30% then the hazard ratio becomes 0.0099 and if the incidence is 20% then the hazard rate is 0.00619.

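### Time to dialysis is tested without adjustment for baseline eGFR, although eGFR is already collected; one pre-specified two-stratum analysis would guard against imbalance and may recover some power

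*Combined protocol and SAP*

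**What the plan says.** Section 8.3.3 sets the test: "The time from randomization to initiation of dialysis will be compared between groups using Kaplan-Meier analysis and the log-rank test for significance". Subjects already on dialysis at entry are left out. The significance rule is "For all secondary endpoint analyses, two-tailed" p below 0.05. The synopsis describes the dialysis analyses only in general terms: "A separate set of similar analyses will evaluate both the need and time to initiating dialysis". Neither place names a covariate, a stratum, or an adjusted or sensitivity analysis of this endpoint.

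On allocation, section 5.3 says "Subjects will be randomized in equal numbers to the following treatment groups" and mentions no stratification factor.

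On baseline renal function, section 6.2 requires: "Obtain baseline laboratory tests including serum Cr and related estimated GFR". Section 4.2.1 gives two entry routes. Route i is eGFR at or below 35 with a decline of at least 10% in 12 months and biopsy-proven IF/TA. Route ii is eGFR persistently at or below 20 ml/min "over the 6 month period prior to enrollment absent other causes for graft dysfunction, and deemed to have a failing allograft". Neither route has a lower limit.

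Sections 2.2 and 8.2 list four secondary endpoints without ranking them: rate of change in GFR, time to dialysis, PRA level and infectious complications.

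**The concern.** Dialysis follows when falling graft function reaches a low level, so the starting eGFR should do much to determine how long that takes. As an illustration, assume decline of 5 ml/min/year and dialysis near eGFR 8. A subject entering at 33 is then (33 − 8)/5 = 5 years away, and one entering at 12 is (12 − 8)/5 = 0.8 years away. The follow-up is 36 months.

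Two things are at stake. First, a log-rank test that ignores a strong prognostic variable can lose power. Second, if the arms happen to differ in mean eGFR, the unadjusted comparison mixes that difference with the treatment effect, and the plan provides no analysis that separates them. Delay of dialysis is part of the research hypothesis (section 1.1) and of the secondary objective (section 2.2). In an open-label trial, an adjustment chosen after an imbalance has been seen would be open to challenge.

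**Working it through.** **The plan's own figure.** No power or event count is given for time to dialysis. The only power figure is 90% for donor-specific antibody, 60% versus 20%, 36 per arm, two-sided 0.05. The uncorrected normal approximation gives z = [0.4·√36 − 1.96·√(2·0.4·0.6)] / √(0.6·0.4 + 0.2·0.8) = (2.400 − 1.358)/0.632 = 1.65, so power is 95.0%. With continuity correction it is 91.7%, and by Fisher's exact test 91.3%. The stated 90% is therefore reproduced, but it says nothing about dialysis.

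**Inputs.** From the documents: the test, two-sided 0.05, 36 per arm (18 per arm in Phase I), 36 months, eGFR at or below 35. Assumed, because the documents do not give them: eGFR distribution, rate of decline, dialysis threshold or rate, treatment effect, and the number left after removing subjects on dialysis at entry (33 per arm in the first model, 36 in the second).

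**Expected imbalance.** If entry eGFR is uniform on 10 to 35, its SD is 25/√12 = 7.2. The SD of the difference in arm means is 7.2·√(2/36) = 1.7 ml/min at 36 per arm and 7.2·√(2/18) = 2.4 at 18 per arm. A difference of 3 ml/min or more then occurs in about 8% and 21% of trials; simulation gave 7–9% and about 21%.

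**Model A, linear decline.** Time = (eGFR − threshold)/slope, 33 per arm, 2,000 to 4,000 trials per scenario. Base inputs: slope mean 5 (SD 3) ml/min/year, threshold 8 (SD 1.5), eGFR measurement SD 1.5. Base-case ranges are across eGFR uniform 10–35 and N(20, 6). The noisier rows use slope SD 5 and threshold and measurement SD 3; the last row uses slope SD 3 with threshold and measurement SD 3.

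| Scenario | Slowing | Unadjusted | 2 strata | 4 strata |
|---|---|---|---|---|
| Base | 30% | 25–28% | 33% | 35–37% |
| Base | 40% | 45–51% | 56–58% | 59–60% |
| Noisier, uniform 10–35 | 30% | 16% | 17% | 16% |
| Noisier, uniform 10–35 | 40% | 25% | 28% | 29% |
| Noisier, N(20, 6) | 30% | 15% | 16% | 17% |
| Noisier, N(20, 6) | 40% | 26% | 26% | 26% |
| eGFR 10–22 | 30% | 30% | 31% | 30% |
| eGFR 10–22 | 40% | 53% | 53% | 53% |

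Repeat runs of the base case agreed to within about 3 points; one paired result (uniform 10–35, 40% slowing) was 46% unadjusted, 55% with two strata and 57% with four.

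**Model B, proportional hazards.** Treatment hazard ratio 0.5, 3,000 trials per scenario, 36 per arm and eGFR 10–35 unless stated. Prognostic strength is the hazard ratio per 5 ml/min lower eGFR.

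| Control dialysis at 36 months | Strength | Unadjusted | 2 strata | Cox, continuous eGFR |
|---|---|---|---|---|
| 60% | 1.0 | 52% | 51% | 51% |
| 60% | 1.5 | 46% | 52% | 53% |
| 60% | 2.0 | 34% | 48% | 54% |
| 40% | 1.5 | 33% | 35% | 34% |
| 40% | 2.0 | 28% | 33% | 34% |
| 80% | 1.5 | 57% | 64% | 67% |
| 80% | 2.0 | 39% | 58% | 68% |
| 60%, eGFR 15–30 | 1.5 | 50% | 51% | 52% |
| 60%, 18 per arm | 2.0 | 18% | 25% | 26% |

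The Monte Carlo standard error near 50% is √(0.25/3000) = 0.9 points, so one-point differences should not be over-read.

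**Type I error.** Over all randomizations in Model B, the unadjusted log-rank rejected in 4.6–5.3% of null trials. Among null trials at 36 per arm with a mean eGFR difference of at least 3 ml/min, it rejected in 8–16% (strength 1.5) or 15–24% (strength 2.0). The two-stratum test rejected in about 3–7% of the same trials. Each conditional figure rests on roughly 0.08 × 3,000 = 240 trials and is approximate.

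**The case against.** The strongest reply is that the plan contains no error. The unadjusted log-rank is a standard, valid test. A reader might infer that chance imbalance inflates the false-positive rate, but that does not follow: over all randomizations the rate is about 5%. The excess appears only conditional on an imbalance, and section 8.3.1 tabulates baseline characteristics, so one could be noticed (although eGFR is not listed there by name). This stands.

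The size of the power loss is also not in the documents. With noisier slopes, thresholds and measurements, or with entry mostly at low eGFR, the gain is close to nil. This stands too, and rules out any claim that a large loss has been shown.

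A reader might also take this to be the main secondary endpoint. Sections 2.2 and 8.2 do not rank the four, and rate of change in GFR comes first. Nor is unstratified randomization stated; section 5.3 is simply silent on the method. Finally, adjustment does not make the endpoint well powered: under most of these assumptions power stays below 60%, and section 8.1 describes the sample size as yielding preliminary data.

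What does not stand is the step from a valid test to no reason for change. The covariate is already measured, its link to dialysis is direct, and the plan offers no other protection against imbalance on it.

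**Conclusion.** The point holds as a specific, inexpensive improvement, not as a flaw that invalidates the analysis. Pre-specified adjustment for baseline eGFR gains from about nil (noisy decline and thresholds, a narrow eGFR range or weak prognosis) to about 5 to 12 points of power in the base linear-decline model. In the proportional-hazards model the two-stratum gain reaches 48 − 34 = 14 and 58 − 39 = 19 points, but only if the hazard doubles per 5 ml/min and at least 60% of controls reach dialysis. The direction is well supported; the size depends on a dialysis rate, eGFR distribution and rate of decline that the documents do not supply.

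The second benefit is interpretive. If the arms are seen to differ in eGFR, the unadjusted result misleads and the stratified one largely does not. The primary antibody endpoint is untouched.

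**What to change.** In section 8.3.3, before any outcome data are reviewed, fix one adjusted analysis as the test for time to dialysis: a two-sided log-rank stratified by screening eGFR, at or below 20 versus above 20 ml/min. Report the hazard ratio and 95% confidence interval from a Cox model stratified on the same factor, noting that it is a within-stratum effect. Keep the unadjusted log-rank and Kaplan-Meier curves as supportive, and align the synopsis wording.

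Use two strata only. Phase II is contingent (section 4.1), so 18 or fewer per arm may remain and four strata would be too thin. The cut at 20 is the protocol's own figure, but it does not separate the entry routes, since a subject below 20 may qualify by either. Strata are also safer than a single linear eGFR term in a Cox model, which was slightly liberal (about 8%) in the linear-decline simulation.

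The cost is a short change of text, with no new data or patients. If eGFR proves not to be prognostic, the loss is about 1 point of power at 36 per arm (52% to 51%).
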